Primary SA1: Determine whether 24 weeks of GnRH_{AG} therapy causes a decline in physical activity when compared with placebo. Change in physical activity energy expenditure (PAEE) from baseline will be measured after 12 (secondary outcome) and 24 wk (primary outcome) of GnRH_{AG} vs placebo therapy. PAEE will be the difference between total daily EE (TEE) measured by the doubly-labeled water technique (DLW) and sleeping EE (SEE) measured by indirect calorimetry, adjusted for the thermic effect of feeding (TEF).¹⁴

H1: PAEE will decrease significantly after 12 and 24 weeks of GnRH_{AG} therapy when compared with placebo.

Secondary SA2: Determine the effects of gonadal function on multiple components of energy expenditure under free-living (DLW) and controlled (metabolic chamber) conditions, including 1) 24-h TEE measured by DLW, and 2) resting EE (REE), SEE, and TEF measured by indirect calorimetry in a metabolic chamber.

H2: When compared with placebo, GnRH_{AG} therapy will cause a decrease in TEE. The relative contributions of REE, SEE, TEF, and PAEE to the decline in TEE will be evaluated.

Secondary SA3: Determine whether the disruption of energy balance in response to GnRH_{AG} therapy leads to unfavorable changes in biomarkers of disease risk, including adiposity, insulin resistance, and inflammation. This will include the measurement of biomarkers in adipose tissue samples.

H3: When compared with placebo, GnRH_{AG} therapy will cause increases in adiposity, insulin resistance, and fasted serum inflammatory cytokines.

Secondary SA4: Because programmed exercise mitigates metabolic consequences of gonadectomy in animals, we will determine whether the bioenergetic and metabolic consequences of GnRH_{AG} in women can be

mitigated through a programmed, supervised exercise intervention (GnRH_{AG} vs GnRH_{AG}+exercise).

H4: Programmed exercise will attenuate the decrease in TEE and the increases in adiposity, insulin resistance, and inflammatory cytokines.

Exploratory Aim: To evaluate the effects of chronic sex hormone suppression and exercise on arterial stiffness and endothelial function. This preliminary data will be used for a new grant application examining the effects of exercise on modulating vascular function in E2-deficient women.

2. Research Strategy

2.a. Significance

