After providing informed consent, volunteers will undergo 2 days of screening tests. Day 1 will include an assessment of depressive symptoms (Center for Epidemiologic Studies Depression Scale (CESD), a clinical laboratory evaluation including a comprehensive metabolic profile, TSH, a complete blood count, and a medical history and physical examination by the study clinician. If volunteers are found to be depressed after administering the CESD (score of >16), the study clinician will administer the Beck Depression Inventory (BDI-II). As score of <18 on the BDI-II will be used along with clinical judgement to determine final eligibility; this approach was used in a previous study completed by [name]. At the second visit, participants will undergo proximal femur and lumbar spine DXA scans to exclude volunteers who have severe low bone mass or osteoporosis (BMD t-scores of <-2.0) because BMD may decrease during GnRH_{AG} treatment. A urine pregnancy test will be done prior to the DXA scan. Afterwards a resting BP and 12-lead ECG will be recorded and then a graded exercise test (GXT), with monitoring of BP and 12-lead ECG, will be administered by research personnel and supervised by a clinician. After screening tests are completed, an enrollment checklist that includes all enrollment criteria will be completed for each volunteer and reviewed by a study clinician and another investigator to verify eligibility.

2.d.6. Randomization and blinding

Volunteers will be informed that they will be randomized to placebo or active GnRH_{AG} and to exercise or no exercise. They will *not* be informed that only women on active GnRH_{AG} will be randomized to exercise. A permuted block randomization with random block sizes will be used for subject assignment into the 3 treatment groups. Randomization will be stratified by age (40-46, 47-60 y). The randomization sequences will be generated by the biostatistician, who will determine the treatment assignment for an individual once study eligibility has been confirmed. The treatment assignment will be given to the research nurse, who will oversee the administration of the placebo (saline) and GnRH_{AG} injections. The nurse will not be responsible for acquisition of study outcomes data; such data will be collected by research staff members who are blinded to drug status. Randomization will occur after eligibility for the study has been determined.

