Limitation of the follow-up testing schedule. For women assigned to the placebo treatment arm, the follow-up tests will not necessarily occur at the same point in the menstrual cycle as the baseline test. Testing will occur during specific time intervals (weeks 10-12, 22-24) to be consistent with the GnRH_{AG} arms. Because this may increase the variance of changes in bioenergetics in the placebo arm, the sample size calculations relied on conservative assumptions (e.g., ability to detect a 25% change in PAEE; use of $\rho = 0.9$; power of 95%).

2.d.10. Data analysis

General Analysis Plan. Data analysis will occur in 4 steps: **1)** Descriptive analyses (including boxplots, scatterplots, profile plots to examine change over time) will be conducted for quality assurance and to assess need for data transformation; **2)** demographic and baseline characteristics of the groups will be compared; **3)** primary and secondary analyses will be completed; and **4)** findings will be assessed for their robustness to issues including the effects of any imbalances in important baseline covariates and the effects of missing data.

Primary Analysis. The primary analysis (**SA1**) will be an intention-to-treat comparison of the differences in the change in PAEE measured after 12 weeks of placebo or GnRH_{AG} therapy. This comparison will be conditioned on the stratification variable, age group (40-46, 47-60y). Statistical inference regarding the difference between treatment groups will be based on the estimated coefficient for a treatment group indicator variable in a linear regression model with 24-week change from baseline as the response variable, and explanatory variables,

including treatment group, age group, and baseline PAEE; the latter is included to improve the precision/power of the inference about treatment differences. The conclusion about statistical significance will be drawn from the linear contrast comparing the placebo and GnRH_{AG} groups.

Secondary Analyses. To address **SA2** and **SA3**, 24-week differences in other outcome measures (24-h TEE, REE, SEE, TEF, PA by accelerometry, measurement of biomarkers in adipose tissue samples, glucose and insulin response to OGTT, serum concentrations of

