inflammatory cytokines, and body composition will be analyzed as above. Secondary analyses will be evaluated for their consistency with the conclusions on the primary endpoint. We anticipate that changes in the secondary outcomes will be consistent (i.e., in terms of biological plausibility) with changes in the primary outcome so that significant differences in the primary endpoint will be reinforced by the secondary analyses. Failure to find biological consistency in primary and secondary endpoints will be taken as evidence that the effects of hormone suppression are not clear and that further study is necessary to resolve inconsistencies. This approach will reduce the risk of false-positive conclusions resulting from multiple statistical tests. **SA4** will be evaluated by ANCOVA as described above, regressing change in PAEE or REE on baseline, age group, and treatment group, adding a linear contrast to compare the GnRH_{AG} and GnRH_{AG}+exercise groups.

Exploratory Aim. Will be evaluated by ANCOVA as described above, regressing change in vascular outcomes (arterial stiffness or FMD) on baseline and treatment group, adding a linear contrast to compare the GnRH_{AG} and GnRH_{AG}+exercise groups.

The characteristics of the time trajectory (at 12 and 24 weeks) for treatment effects will also be determined in secondary analyses. These analyses will evaluate the biological plausibility of the time trajectory (i.e., a biologically-meaningful time trend) to rule out false positive conclusions in the primary analysis. Evaluation of the time trajectory will also motivate future studies of mechanisms and methods to improve longer-term outcomes. The analytic methods to be used for evaluation of the time trajectory include a mixed-effects model with time as a fixed covariate to estimate the mean effect at each measurement time,⁹³ conditioned on the stratification variable and the baseline value of the outcome variable.

2.d.11. Data management

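### The Exploratory Aim model for the vascular outcomes omits the age stratum used in randomisation, which may cost some precision; the same sentence should also state both contrasts

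*Combined protocol and SAP*

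**What the plan says.** Section 2.d.6 fixes the design: "Randomization will be stratified by age (40-46, 47-60 y". Section 2.d.10 carries that factor into three models.

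- **Primary Analysis:** "This comparison will be conditioned on the stratification variable, age group (40-46, 47-60y".
- **SA4:** the aim "will be evaluated by ANCOVA as described above", "regressing change in PAEE or REE on baseline, age group, and treatment group".
- **Time trajectory:** the mixed-effects model conditions on the stratification variable and the baseline outcome value.

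The Exploratory Aim paragraph comes directly after SA4 and opens with the same reference back to the ANCOVA above. Its model is "regressing change in vascular outcomes (arterial stiffness or FMD) on baseline and treatment group", "adding a linear contrast to compare the GnRH_{AG} and GnRH_{AG}+exercise groups". It lists no age group, gives no reason for the difference, and spells out only the exercise contrast.

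The aim in section 1 is broader: "To evaluate the effects of chronic sex hormone suppression and exercise on arterial stiffness and endothelial function". Its stated use is narrower: "This preliminary data will be used for a new grant application examining the effects of exercise on modulating vascular function".

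**The concern.** When randomisation is stratified on a factor, the analysis normally conditions on it. If the factor predicts the outcome and is left out, its variance stays in the error term and the interval for the treatment effect is wider than it need be. The vascular sub-study is optional and so cannot be larger than the parent trial. Its purpose is to supply estimates for a later application, so precision is what it has to offer.

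The wording also leaves room for doubt. SA4 refers back to the ANCOVA above and still lists age group. The next paragraph refers back in the same way and does not list it. Two analysts could follow this text and fit different models. They could also differ on whether to report placebo versus GnRH agonist for the vascular outcomes.

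**Working it through.** **The plan's own figure.** The only sample-size calculation (section 2.d.4) is for PAEE. The SD of change is sqrt(2 × (1 − 0.90)) × 330 = 147.6, stated as 148. With 15 per group, a difference of 200 and two-sided alpha 0.05 (sidedness assumed), noncentral-t power is 95.1% with the three-group error (42 df) and 94.6% with a two-group t test. The stated 95% reproduces. It says nothing about the vascular outcomes, for which the documents give no SD, effect size, age effect or sub-study size.

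**Inputs for this point.**
- Model as written: intercept, two treatment terms and baseline, so N − 4 error df.
- Model with age group: one more term, so N − 5 error df.
- R2, the share of residual variance explained by age group: assumed, 0 to 0.20.
- N: 66 (3 × 22) is full enrolment and therefore a ceiling; 45 (3 × 15) is the powered number; 30 (3 × 10) is assumed for a smaller sub-study.

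**Formula.** With arms balanced within strata, the ratio of interval widths, age omitted to age included, is approximately

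sqrt(1/(1 − R2)) × t(0.975, N − 4) / t(0.975, N − 5).

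For N=45 and R2=0.10: sqrt(1/0.90) = 1.0541, the t ratio is 0.9992, and the product is 1.053.

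| R2 (assumed) | N=30 | N=45 | N=66 |
|---|---|---|---|
| 0 | 0.998 | 0.999 | 1.000 |
| 0.02 | 1.008 | 1.009 | 1.010 |
| 0.05 | 1.024 | 1.025 | 1.026 |
| 0.10 | 1.052 | 1.053 | 1.054 |
| 0.20 | 1.116 | 1.117 | 1.118 |

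Seen the other way, adding age group at R2=0.20 and N=45 narrows the interval by 1 − 1/1.117 = 10.5%. N hardly matters; R2 decides.

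**Simulation check.** There were 4,000 trials per setting with 10, 15 or 22 per arm, testing the exercise contrast under no effect. The first block has strata balanced across arms. The second lets stratum vary at random, independent of arm.

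| Strata | R2 | Width ratio | Type I error, age omitted |
|---|---|---|---|
| Balanced | 0 | 0.997–1.000 | 0.044–0.052 |
| Balanced | 0.05 | 1.026–1.027 | 0.040–0.042 |
| Balanced | 0.10 | 1.056–1.057 | 0.041–0.044 |
| Balanced | 0.20 | 1.122–1.131 | 0.026–0.031 |
| Not balanced | 0 | 0.979–0.991 | 0.048–0.049 |
| Not balanced | 0.05 | 1.005–1.017 | 0.044–0.054 |
| Not balanced | 0.10 | 1.030–1.046 | 0.047–0.055 |
| Not balanced | 0.20 | 1.098–1.111 | 0.049–0.052 |

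The Monte Carlo standard error near 0.05 is sqrt(0.05 × 0.95/4000) = 0.003. The test is conservative only with balanced strata and an age effect. Without balance the error rate is nominal, and the intervals are still wider once R2 reaches 0.10.

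**The contrasts.** Section 2.d.4 describes the trial's analysis as an ANOVA with two contrasts: placebo versus GnRH agonist, and GnRH agonist with versus without exercise. The Primary Analysis paragraph names the first again. The Exploratory Aim paragraph names only the second.

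**The case against.** A reader might infer that the vascular intervals are certainly too wide and the test certainly conservative. The documents do not support that. Loss of precision requires age group to predict vascular change after baseline adjustment, and nothing in the plan gives such an effect. At R2=0 there is no loss, and omission is very slightly better. Conservatism also requires balance across arms within strata. Blocked randomisation gives that for the parent trial, but section 3.1.a says sub-study volunteers are recruited from among the parent participants, with no stratification of their own. This part of the objection stands.

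A reader might also infer that the suppression half of the aim has no test, or will not be estimated. That goes too far. Section 2.d.4 names both contrasts. The verb in "adding a linear contrast to compare the GnRH_{AG} and GnRH_{AG}+exercise groups" can be read as putting a second contrast alongside the one already described. A three-group model yields the placebo versus GnRH agonist difference in any case. This too stands, and it reduces the contrast point to wording.

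The reference back to the ANCOVA above might carry the age term over as well. That is possible but less convincing, because SA4 uses the same reference and still lists the term. Step 4 of the General Analysis Plan, on robustness to baseline imbalances, offers partial cover for age imbalance. It is a sensitivity check and does not specify the main vascular model.

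**Conclusion.** As written, the vascular model leaves out the factor the trial randomises by, with no reason given, while the plan's primary, SA4 and time-trajectory models condition on it. The consequence is a possible loss of precision. Intervals are wider by about 0%, 2.5%, 5% or 12% if age group explains 0, 5, 10 or 20% of residual variance, and those R2 values are assumptions. If stratum balance does not survive in the sub-study, adjustment has the further merit of correcting chance age imbalance between arms. No bias and no excess of false positives is shown. The missing placebo contrast is incomplete wording in one paragraph, not an absent analysis. Severity is low: the aim is exploratory, the contrast the paragraph does name is the one the planned application needs, and no primary or secondary conclusion depends on this model.

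**What to change.** In the Exploratory Aim paragraph of section 2.d.10, list the terms as baseline, age group and treatment group, matching SA4. In the same sentence state both contrasts from section 2.d.4: placebo versus GnRH agonist, and GnRH agonist versus GnRH agonist plus exercise. Make the change before the vascular data are analysed.

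The cost is one sentence and one degree of freedom. If age group has no effect, the intervals widen by about 0.1–0.2% at N=30–45 by the formula. With strata unbalanced by chance, the simulated cost at R2=0 is about 1–2% (1/0.991 to 1/0.979). No trial procedure changes.

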Although the GnRH_{AG} will be administered to participants in a blinded manner, it is acknowledged that participants may be aware of treatment status because of the cessation of menses that typically occurs. Participants will be informed that menstrual cycles may stop either because of the drug intervention or because they are approaching the age of menopause. Participants will be further informed that menstrual cycles may not resume or may be irregular after the completion of the intervention because they are approaching the age of menopause. We are aware of one study suggesting that menstrual cycle function may not resume in older pre-/perimenopausal women following GnRH_{AG} therapy if the pretreatment serum FSH level measured during days 3 to 5 of the follicular phase is >25 mIU/mL.⁶⁷ We will exclude volunteers who meet this criterion because of the possibility that this may be an early harbinger of the menopause.

2.d.7. Interventions

Drug intervention. The drug intervention will be monthly intramuscular injections of placebo (saline) or leuprolide acetate (3.75 mg for depot suspension; Abbott Laboratories; Abbott Park, IL) for 24 weeks. One-third of participants will be randomized to receive placebo and two-thirds will receive GnRH_{AG}. Absence of pregnancy will be confirmed before each dosing. A single injection of leuprolide acetate produces an initial stimulation (for up to ~2 wk) followed by a prolonged suppression of pituitary gonadotropins and ovarian hormone secretion; repeated monthly dosing maintains the suppression of ovarian function. Leuprolide acetate has been used clinically for up to 1 year without serious adverse events, although there may be a decrease in BMD that recovers slowly following cessation of treatment.^{68,69} Side effects are those typical of estrogen deficiency. In studies of women with uterine fibroids, GnRH_{AG} 3.75 mg/mo induced amenorrhea in 61%, 86%, and 90% of women after 1, 2, and 3 mo of treatment, respectively.^{70,71} Return of menses typically occurred

within 2-3 mo of cessation of therapy. The **rationale** for the drug regimen is that this standard clinical dose suppresses ovarian function and results in fat gain after 24 weeks of treatment.^{9,10}

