
Women in the placebo group may progress to peri-menopausal status during the 6-month intervention (they cannot become postmenopausal by definition of absence of menses for 12 months) and may, therefore, have a decline in PAEE. This was taken into account by using conservative for statistical power and sample size calculations. Secondary data analyses will also be performed that include only women who maintain premenopausal status over the period of intervention.

The potential effects of GnRH_{AG} therapy to reduce PAEE could be mediated by a number of factors not being thoroughly studied in this project (e.g., sleep disturbance secondary to the expected increase in menopausal symptoms in women on GnRH_{AG}). The Ancillary Projects program of the SCOR could support the addition of some outcomes measures, but careful consideration will be given to the impact on subject burden before any ancillary projects are approved.

3. Protection of human subjects

The proposed study meets the definition of a clinical trial in that it is a prospective biomedical research study of human subjects that involves random assignment to pharmacologic and behavior intervention groups. However, we consider it to be clinical research on a relatively small number of subjects, rather than a 'clinical trial' because it is designed to reveal mechanistic consequences of the loss of ovarian function. It is not a Phase III clinical trial.

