3.1 Risks to human subjects

a. Human subjects involvement, characteristics, and design

Volunteers who are eligible and willing to participate will undergo the intervention protocol and procedures described in the Research Plan. We plan to enroll 66 volunteers in the study. They will be healthy, eumenorrheic premenopausal women, aged 40 to 60 years. Eumenorrheic premenopausal status is defined as not yet reaching the Early Menopausal Transition Stage -2 by the Stages of Reproductive Aging Workshop (STRAW) criteria.⁹⁹ Stage -2 is characterized by a change in cycle length of 7 or more days (e.g., regular cycles every 24 days instead of 31 days). Accordingly, the medical history will query for cycle regularity in the past year and whether cycle length has changed. The investigators debated whether to have an exclusion criterion for participation in regular exercise. In the absence of knowledge as to whether women who exercise

regularly may be more or less susceptible to the potential effects of gonadal function to regulate physical activity, it was decided that this should not be too restrictive. Thus, only women who exercise at least 30 minutes per day at a moderate to vigorous intensity most days of the week (defined as >4 d/wk) will be excluded. The prospective cohort study that supports a decline in PAEE during the menopausal transition did not have an eligibility criterion based on physical activity level.¹² The investigators also debated whether there should be an exclusion criterion for body mass index (BMI). The prospective cohort study did not have one.¹² That paper did not report BMI, but fat mass averaged ~40% of body weight. In our experience, that falls into the 'obese' category by BMI. Based on this, we chose the exclusion threshold as a BMI $\geq 40 \text{ kg/m}^2$.

Inclusion criteria

Volunteers will be women aged 40 to 60 years who are still experiencing regular menstrual cycles. They must be willing to be randomized to placebo or GnRH_{AG} therapy for 24 weeks. They must be physically able and willing to be randomized to participate in a supervised exercise training program. Volunteers for the Vascular sub-study will be recruited from the larger group of participants in the parent study.

Exclusion criteria

Volunteers will be excluded from participation for the following:

- irregular menstrual cycles defined as 2 or more missed cycles in the previous year
- serum FSH >25 mIU/mL measured during the first 5 days of the menstrual cycle

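### The secondary analysis limited to women who stay premenopausal cannot be formed alike in all arms, because leuprolide removes the cycle pattern that defines the status

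*Combined protocol and SAP*

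**What the plan says.** Section 2.d.14 (Potential Limitations) raises the possibility that the comparator drifts: "Women in the placebo group may progress to peri-menopausal status during the 6-month intervention" "and may, therefore, have a decline in PAEE". It says the power assumptions already allow for this, and then adds: "Secondary data analyses will also be performed that include only women who maintain premenopausal status over the period of intervention". No arm, outcome or time point is named, and no rule is given for deciding who qualifies.

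Section 3.1.a supplies the only definition of the status: "Eumenorrheic premenopausal status is defined as not yet reaching the Early Menopausal Transition Stage -2", and "Stage -2 is characterized by a change in cycle length of 7 or more days".

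For women on the drug, three places matter:
- Section 2.d.7 reports that in women with fibroids the study dose "induced amenorrhea in 61%, 86%, and 90% of women after 1, 2, and 3 mo of treatment, respectively".
- Section 3.1.c (Potential risks) says regular menses should cease during treatment.
- Section 2.d.14 says the agonist gives low gonadotropins, where menopause gives high ones.

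The analysis section (2.d.10) makes the primary comparison intention-to-treat and does not mention the subset. It also says that secondary analyses will be judged for consistency with the primary conclusion and are expected to reinforce it.

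**The concern.** The subset depends on a status that can be followed in one arm out of three. A woman on leuprolide whose periods stop has shown the effect of the drug. Her cycles no longer reveal whether she would have stayed premenopausal without it. The rule therefore cannot select comparable women from each arm.

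If placebo women alone are filtered, one randomised group is trimmed on an event after randomisation, while the women in the other groups who would have had the same event stay in. The trimmed women are those who, by the protocol's account, may decline in PAEE, so the placebo mean change rises and the contrast widens in the hypothesised direction. The risk is that such a result is then counted as support for the primary finding under the consistency argument in section 2.d.10.

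**Working it through.** **1. The plan's own figures.** Section 2.d.4 assumes baseline PAEE of 800 kcal, SD 330, correlation 0.90 and a 25% effect.
- SD of change = √(2 × (1 − 0.90)) × 330 = 147.6, stated as 148.
- Effect = 0.25 × 800 = 200 kcal/d.
- Two-sided power at 15 per group is 94.6% (t test, 28 df) or 95.1% (42 df, three-group error term).

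The stated 95% reproduces and is not in dispute. It serves here only as a scale.

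**2. Can the status be observed on the drug?**
- By cycle length: no. Menses are expected to stop, with 90% amenorrhea at month 3.
- By raised FSH: no. Gonadotropins are low on the agonist.
- By study records: the monthly visit in section 2.d.9.2 lists no cycle record and no hormone measurement. Even for placebo, the plan does not say how progression would be detected.

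**3. Literal application to all arms.** Women still menstruating on the drug: 22 × (1 − 0.90) = 2.2 per GnRH agonist arm enrolled, or 15 × 0.10 = 1.5 per arm evaluable. These would be the incompletely suppressed women, so the contrast is unusable and could lean toward no effect.

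**4. Placebo-only application.** If a share p of placebo women progress and each declines by d, removing them raises the placebo mean change by about p × d. The documents give neither quantity for this trial. The cited cohort of the menopausal transition (sections 1 and 2.a) allows a rough scale.
- Share progressing: 34 of 129 women were still premenopausal at 4 years. At constant hazard, p over 6 months = 1 − (34/129)^(1/8) = 15.4%. If linear, p = (95/129)/8 = 9.2%. That is about 2 to 3 of 22 placebo women.
- Decline: section 2.a gives a fall of more than 50% over 4 years, and section 1 gives 55% over 3 years. Assuming linearity, and carrying an accelerometer percentage over to 800 kcal of PAEE, d = 400/8 = 50 to 440/6 = 73 kcal/d per 6 months.
- Shift: 0.092 × 50 = 4.6 to 0.154 × 73 = 11 kcal/d, or about 2 to 6% of 200.
- Standard error of the contrast at 22 per arm: 148 × √(2/22) = 44.6 kcal/d. The shift is about 0.1 to 0.25 of one standard error.
- Upper case, every progressor losing the full 200: 0.154 × 200 = 31 kcal/d, or 15% of 200.

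**5. Effect on the test if the shift is spurious.** Assume no drug effect, the same share declining in both arms for non-ovarian reasons, 22 per arm and SD 148. With d = 200, simulation (5,000 runs) puts two-sided rejection near 5% without the filter and at about 9% with it when p is about 15%. With d = 100 at the same p, a noncentral t calculation gives 6.2%. At the cohort-scaled decline of 50 to 73 it would be lower still.

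**The case against.** The strongest reply is that the filter removes dilution and is not bias. The study asks what loss of ovarian function does. A placebo woman who enters the transition has partly received the exposure, so leaving her out brings the contrast nearer to suppressed versus intact function. Her counterparts on leuprolide are suppressed whatever their natural stage, so keeping them adds nothing false. This stands if the decline in progressing women is ovarian. It fails if the decline comes from ageing, sleep or other causes, because those causes act in the leuprolide arms too. The plan has no means of separating the two, and in either case randomisation no longer protects the comparison.

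It can also be said that section 3.1.a defines status by natural reproductive stage, so drug-induced amenorrhea should not count as leaving it. That is a fair reading, but it leaves the status unobservable on the drug and leads to the placebo-only form.

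Three stronger readings are tempting, and the documents do not support them:
- A reader might infer that the main result is compromised. The primary analysis is intention-to-treat, and nothing lets the subset replace it. Section 2.d.14 offers the subset in addition to the conservative power assumptions.
- A reader might infer that a larger drug effect is built in. The text says only that these women may progress and may decline, and it never states that the filter is for placebo alone. That form is an inference from what is workable and from the sentence about placebo women that introduces the rule.
- A reader might infer a large distortion, such as 0.30 × 200 = 60 kcal/d. That needs 30% to progress in 6 months and each to lose the whole planned drug effect. The cohort figures point far lower, and the exclusion of FSH above 25 mIU/mL may reduce progression further.

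**Conclusion.** The point holds as a defect in one secondary analysis. No wording of the rule makes premenopausal status observable on leuprolide, and no version of the comparison keeps the arms as randomised. The direction, toward a drug effect, applies to the placebo-only form and rests on the protocol's premise that progressing women lose PAEE. How much of the shift would be spurious cannot be determined from the plan.

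The likely size is small: about 5 to 11 kcal/d on cohort-scaled assumptions (constant or linear progression, linear decline, accelerometer percentages applied to PAEE), rising to about 31 kcal/d in the upper case. The point deserves correction because section 2.d.10 treats agreement of secondary analyses as reinforcement, and it does not exclude this one. Severity: minor to moderate.

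**What to change.** Do one of two things in section 2.d.14, and carry it into section 2.d.10:
- Delete the subset comparison and report the number of placebo women who progress, with their PAEE changes, descriptively.
- Or restate it as a placebo-only, non-randomised sensitivity analysis. It keeps all GnRH agonist women, states how progression is ascertained in placebo women, appears beside the intention-to-treat estimate with the number of progressors, and is expressly excluded from the consistency argument in section 2.d.10.

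Optionally, add an exploratory treatment interaction with a marker fixed before randomisation and available in every arm, such as baseline FSH (already required for eligibility) or the age stratum (already in the model). The text should say that this tests effect modification, which is a different question from contamination of the comparator, and that it will be imprecise at 22 per arm.

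The cost is a few sentences. Deletion needs no new data. The restated version needs a simple cycle record for placebo women if none is kept, collected in all arms so as not to reveal assignment.
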